Aim 2: To determine how slightly-thick and mildly-thick liquids flow and whether they reduce aspiration compared to thin liquids in patients with base of tongue cancer. We will collect concurrent videofluoroscopic x-rays of swallowing and physiological measures of tongue pressure in patients with head and neck cancer using thin, slightly- and mildly-thick liquid barium stimuli. This appointment will occur approximately 3-6 months after the completion of the participants' radiation schedule. Significance: This will demonstrate the impact of consistency on bolus flow through the mouth and pharynx, controlling for the forces used to initiate flow and propel the bolus. Additionally, the data collected will aid in characterizing swallow physiology after completion of radiation therapy.

Aim 3: To determine whether the use of starch vs. gum thickeners impact the results of aims 1 and 2
The thickened liquids used for aims 1 and 2 will be prepared using both starch- and gum-based thickeners. Additionally, we will collect measures of salivary flow to control for possible interactions between thickener type and oral dryness on the results. Significance: Individuals may find one thickener more palatable or comfortable to swallow. Understanding this may impact compliance, swallowing safety and quality of life.

3. Methods

Participants:

The protocol will involve a single sample of adults, aged 18 or older with an initial cancer diagnosis of base of tongue cancer (T1-T3, N0-N2c, HPV + or -). The eligibility criteria will include completion of bilateral radiation therapy to the neck 3 months prior to enrollment, and removal of enteral feeding tube.

Participants will be asked to attend appointments and complete all data collection sessions described in this protocol. Participation involves two appointments, and two follow-up phone calls.

Exclusion Criteria:

- Participants will be accepted into the study provided they have no previous health condition known to cause swallowing impairment (e.g., stroke; brain injury; neurodegenerative disease).
- Individuals with a previous history of radiation to the head and/or neck area (prior to the current radiation treatment) will be excluded from this study given the possibility of long-term radiation effects to the swallowing apparatus.
- Individuals with a previous cancer diagnosis will be excluded from the study.

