- Participants who do not show impaired swallowing safety on thin liquids in the videofluoroscopy (Penetration Aspiration Scale scores of 1 and 2) will be withdrawn from the study.
- Participants who have had, or have a planned neck dissection will be excluded.
- Individuals with tracheostomy *in situ* will be excluded from the study.
- Individuals with cognitive communication difficulties that preclude the understanding of the protocol or following study instructions will be excluded from the study.
- Due to the requirement to swallow stimuli containing starch based thickeners, which carry a significant carbohydrate load, individuals with Type 1 Diabetes will be excluded.
- Individuals with known allergies to latex, dental glue or barium will be excluded, due to the probability that these items will come into contact with the oral mucosa during data collection.
- Children and pregnant women will be excluded from the study due to the use of radiation
- Occupational exposure to radiation exceeding half the limit specified for Ontario exposed workers within the past 12 months.

These exclusion criteria will be confirmed using a self-report questionnaire form at the time of intake into the study (see standard operating procedures [SOP], provided as an additional study document). Any questions will be clarified through discussion with the research assistant responsible for participant intake, and, where necessary with the principal investigator.

Recruitment:

This is a preliminary study that will demonstrate feasibility for a future planned extension. We propose to recruit 10-12 participants. Potential participants will be identified by study Co-PIs [name] and [name] through the current radiation therapy clinics and base of tongue cancer caseloads at Princess Margaret Cancer Centre.

Stimuli:

An array of barium and non-barium stimuli has been developed for this study. These stimuli include thin, slightly-thick and mildly-thick liquids, defined using the International Dysphagia Diet Standardisation Initiative (IDDSI) gravity flow measures. The barium stimuli used for videofluoroscopy will be prepared using E-Z-Paque® barium in 20% w/v barium concentration with starch and gum-based thickening agents (Nestlé Resource® ThickenUp® and ThickenUp Clear®). The non-barium stimuli will be prepared using Nestle's Lemon Splash® lemon-flavoured water and the same starch and gum-based thickening agents

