- j) Responses to follow-up phone calls exploring acceptance of thickened liquids.

Data Collection Procedures: Data Collection Session 1: The participant will arrive at the lab and will be asked to complete two questionnaires: the MD Anderson Dysphagia Inventory (MDADI), the Performance Status Scale for Head and Neck Cancer (PSS-HN) and the University of Washington Quality of Life Revised Version 4 (UW-WOL-R4).

Prior to data collection, saliva flow will be collected using the Saxon Test, for which the participant will chew on folded sterile gauze for 2 minutes. The gauze will be weighed before and after chewing to determine amount of saliva production. The participant will then be asked to swallow 6 non-barium

stimuli, and 2 barium stimuli thickened using starch and xanthan-gum based thickeners. After the participant has sampled each stimulus, they will be asked to rate palatability on a visual, hedonic scale (see study instruments provided).

Data Collection Session 2: Prior to data collection, saliva flow will be collected using the Saxon Test, for which the participant will chew on folded sterile gauze for 2 minutes. The gauze will be weighed before and after chewing to determine amount of saliva production. The participant will then be seated in the videofluoroscopy suite for tongue pressure sensor attachment. A silicon strip housing three 8 mm diameter pressure bulbs will be attached in midline to the roof of the participant's mouth, with the front sensor located immediately behind the participant's upper incisor teeth. The sensor strip will be attached using a medical adhesive (Stomahesive®, Convatec, St-Laurent, Quebec, Canada).

Following sensor attachment, the video output line from the fluoroscopy unit and the tongue pressure sensors will then be connected to the KayPENTAX Digital Swallowing Workstation Swallowing Signals Lab equipment, which is located on a properly insulated cart with an uninterrupted power supply and isolation transformer (see Image 1). If the participant is unable to tolerate the attachment of the sensors due to mucositis or general discomfort, we will measure tongue strength using the Iowa Oral Performance Instrument (IOPI) and collect the videofluoroscopy measures without the use of the adhered sensors.

Image 1. Tongue pressure sensors.

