Participants will be asked to swallow a series of thin, slightly-thick and mildly-thick barium stimuli 1 (3 boluses each of 5 stimuli, for a total of 15 boluses) in videofluoroscopy, with concurrent measurement of tongue-palate pressure. Videofluoroscopy will be performed at optimal temporal resolution (30 pulses/second) and captured at 30 frames/second. The stimuli will be presented in a randomized design, blocked by stimulus type. Participants will be allowed to take natural sized sips of each stimulus from cups containing 40 ml. Sip volume and mass will be calculated, by weighing the cups prior to and after the videofluoroscopic assessment.

Data Processing:

The tongue-pressure waveform will be segmented using an automatic segmentation algorithm developed previously in the PI's lab. Similarly, the videofluoroscopy recordings will be spliced into single bolus clips and the audio channel will be muted to remove cues that might bias rating. Blinded videofluoroscopy rating will then be performed in duplicate by trained raters in the [name] Lab following established procedures (see SOP provided as an additional study document). Discrepancies between raters will be flagged and resolved at consensus meetings, as required. These procedures will yield a

large number of parameters for each swallow. We will use established measures within our lab to collect and analyze measures related to kinematics and residue.

[figure not shown]
Follow-up phone calls: If deemed appropriate, the participant may be offered the opportunity to complete a follow-up component. For those willing to participate, this optional experiment will involve two follow-up telephone calls (at 2 weeks and 3 months following the videofluoroscopy) to determine compliance with use of thickened liquids recommended following the videofluoroscopy (see study instruments provided for questionnaires).

Data Analysis:

For Aim 1, we will compare hedonic ratings for the different stimuli using a univariate ANOVA. It is hypothesized that ratings will be significantly better for the thin and slightly thick stimuli compared to the mildly-thick stimuli, and that a preference will be seen for the gum compared to the starch thickened liquids.

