For Aim 2, blinded videofluoroscopy rating will be performed in duplicate, and discrepancies between raters will be flagged and resolved at a consensus meeting. The frequency of aspiration will be explored with the thin stimuli and compared to the prevalence of aspiration when thickeners are introduced using chi-square statistics.

We will model the impact of stimulus on two timing measures of pharyngeal bolus flow from the videofluoroscopy (i.e., a) the interval from the bolus passing the mandibular ramus until laryngeal vestibular closure; b) the interval from the bolus passing the mandibular ramus until entering the upper esophageal sphincter) and on measures of post-swallow residue (Normalized Residue Ratio Scale). The Saxon test results regarding oral dryness will be used as a covariate for all analyses, as illustrated in the Figure below:

A path analysis approach will be used to first identify differences in tongue pressure across stimuli

(Question 1). If confirmed, this potential modulator will be added to the Question 2 model as a covariate (Question 3). The planned analyses will involve linear mixed model repeated measures ANOVAs with a factor of stimulus.

For Aim 3, we will use qualitative methods to describe participant reports of adherence to the prescribed thickener. Information from the quality of life and performance status scales collected in session 1 will be used to inform our understanding of variations on patterns of thickener acceptance.

4. Risks and Benefits

Risks

The following risks will be disclosed to all participants prior to obtaining their consent to participate:

- a) Participants may experience local mucosal irritation from the glue on the adhesive strip used to attach the tongue-pressure bulbs for data collection. The glue usually wears off within 90 minutes following the conclusion of data collection. In the incidence that participants are unable to tolerate the attachment of the sensors, we will use the IOPI tongue bulbs to collect tongue measurements, and collect videofluoroscopic data using the same protocol.
- b) Participants may dislike the taste or texture of some of the thickened liquid stimuli in the study. Participants will be reminded that they are free to discontinue participation at any time.

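### Tongue pressure enters the Aim 2 flow model as one covariate without separating within-person from between-person variation, so the force-controlled stimulus effect may be biased in either direction

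*Combined protocol and SAP*

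**What the plan says.** Section 3, Data Analysis, sets out a sequence of models for Aim 2. First: "A path analysis approach will be used to first identify differences in tongue pressure across stimuli" (Question 1). If a difference is confirmed, "this potential modulator will be added to the Question 2 model as a covariate" (Question 3). On the model family: "The planned analyses will involve linear mixed model repeated measures ANOVAs with a factor of stimulus". Section 2, Aim 2, says what the adjusted result is for: the impact of consistency on bolus flow, "controlling for the forces used to initiate flow and propel the bolus".

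The data behind the covariate are described under Data Collection Session 2: "3 boluses each of 5 stimuli, for a total of 15 boluses", taken "with concurrent measurement of tongue-palate pressure". On sample size, Recruitment says: "We propose to recruit 10-12 participants". Participants who cannot tolerate the adhered sensors have tongue strength measured with the IOPI instead, and their videofluoroscopy proceeds without the sensors.

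The plan does not mention centring, a participant-mean term, random effects or a covariance structure. The Saxon test is a further covariate, but it measures oral dryness and does not separate the two pressure slopes.

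**The concern.** Every participant is meant to swallow all five stimuli, so the stimulus contrast is within-person. To remove the part of that contrast that runs through propulsive force, the model must know how flow changes when the same person pushes harder. That is the within-person slope. The between-person slope answers another question: whether people with higher pressure on average have different flow. It also carries whatever else distinguishes those people, such as age, tumour extent or radiation damage.

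A random-intercept model with one pressure term estimates a weighted average of the two. If they differ, the Question 3 stimulus effect is adjusted by the wrong amount, and the output of a one-slope model does not show it. At stake is the reading of Question 3: how much of the consistency effect remains once force is held constant.

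**Working it through.** The plan gives no effect size, SD, ICC or alpha, so there is no stated figure to reproduce beyond 3 x 5 = 15 boluses, which is correct.

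**Inputs from the protocol.** N = 10-12 (11 used); m = 15 swallows; 5 stimuli.

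**Assumed, not in the documents.** Within-person pressure SD 1 and residual SD 1; within-person slope bW = -0.5; between-person slope bB = 0, -0.5 or -1; between/within SD ratio r = 1 to 3; outcome ICC 0.3 to 0.7; pressure higher by D = 1 within-person SD for the mildly-thick stimuli; true direct stimulus effect 0; participant random intercept. The five stimuli are taken as thin plus starch and gum versions of the two thickened levels.

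**Formulae.**
- Single slope: b = w·bB + (1 - w)·bW.
- Weight: w = L·SSB / (L·SSB + SSW).
- SSB = m(N - 1)(r² + 1/m) = 150r² + 10.
- SSW = N(m - 1) - 4 = 150, after 4 degrees of freedom for stimulus.
- L = 1/(1 + m·t), where t is the between-person to residual variance ratio seen by the fitted model: t = ICC/(1 - ICC) + (bB - b)²r². The second part arises because the random intercept absorbs the slope mismatch; b and t are solved together.
- Left in the stimulus contrast, in absolute size: w·|bW - bB|·D.

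**Smallest case** (r = 1, ICC 0.7, bB = 0). t = 2.33 + 0.487² = 2.57; L = 1/(1 + 38.6) = 0.0253; L·SSB = 0.0253 x 160 = 4.04; w = 4.04/154.04 = 0.026; b = -0.487. Left behind: 0.026 x 0.5 = 0.013.

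**Largest case** (r = 3, ICC 0.3, bB = 0). t = 0.43 + 0.371² x 9 = 1.67; L = 1/(1 + 25.0) = 0.0384; L·SSB = 0.0384 x 1,360 = 52.2; w = 52.2/202.2 = 0.26; b = -0.37. Left behind: 0.26 x 0.5 = 0.13.

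**Simulation at the same settings:**

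| Between slope | Single slope | Effect on the stimulus contrast |
|---|---|---|
| 0 | -0.49 to -0.37 | 2% to 26% of the force part stays |
| -0.5 (equal) | -0.50 | none |
| -1 | -0.51 to -0.64 | over-corrects by up to 0.14/0.5 = 28% |

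With pressure split into deviation and mean, the within-person slope stays near -0.50 throughout.

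**Against the noise.** Mildly-thick (6 x 11 = 66 swallows) versus thin (3 x 11 = 33), adjusted for pressure: SE = √(1/66 + 1/33 + 1/150) = 0.23. The bias is therefore 0.01/0.23 = 0.04 to 0.13/0.23 = 0.57 of a standard error.

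**Fewer swallows.** Section 4, items d and e, ends the session on observed aspiration and soon after a 2-minute bell. Expected exposure there is 118+/-18 seconds, from healthy adults. If that is a mean and SD of a normal distribution, 120 seconds lies 2/18 = 0.11 SD above the mean, so about 46% would reach the bell. Holding t at ICC/(1 - ICC), with N = 12, ICC 0.5 and variance ratio 1 to 4, w is 0.06 to 0.20 at 15 swallows and 0.20 to 0.47 at 5. In simulation with r = 1 to 3 and ICC 0.3 to 0.7, the share left behind rises to 3-36% if half the participants stop after 4 to 11 swallows (assumed), and to 4-55% if all do. The split model's slope stays at -0.48 to -0.51.

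**The case against.** **The plan does not say raw.** It says only that pressure is added as a covariate. It does not say whether it is centred, averaged by stimulus or taken from one of the three bulbs, and the random intercept is my assumption. With participant as a fixed effect there would be no blend. The figure that Data Analysis refers to is missing from the text available to me. This stands: the point is an unspecified step whose plain reading is one slope, not a stated wrong choice. If the figure or a separate document splits the term, the point falls.

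**The direction is unknown.** A reader might infer that part of the force effect necessarily remains in the stimulus effect. The documents do not support that. It requires the between-person slope to be weaker than, or opposite in sign to, the within-person one. Equal slopes give no bias and a steeper between-person slope over-corrects. Nothing in the protocol says which applies.

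**It is small, conditional and exploratory.** With complete sessions the bias stays below 0.6 of a standard error. The covariate enters only if Question 1 is positive, and this is a feasibility pilot. This also stands and limits the importance of the point. It does not remove it, because the pilot is meant to support a planned extension that may inherit the model.

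**The remedy is not free.** A reader might take the split to cost nothing. It uses a person-level degree of freedom, and the deviation is undefined for IOPI participants. In shortened sessions a participant's mean also depends on which stimulus blocks were completed, although the simulated split slope held up.

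**Conclusion.** The concern holds as a gap in specification. One slope on a covariate that varies at two levels is the plain reading of Question 3. Under a participant random intercept, that slope adjusts the stimulus effect correctly only if the two slopes coincide. The protocol gives no reason to assume that they do, and no figures to predict the sign of any error.

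With full sessions the error is modest, because 15 swallows per person make the model lean on within-person information. It becomes more material when the ICC is low, when people differ widely in pressure, or when swallows are lost. All sizes rest on the assumed slopes, SD ratios and ICCs above. This is a worthwhile refinement; it would not overturn a feasibility conclusion.

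**What to change.** In Data Analysis, Aim 2, state that for Question 3 tongue pressure enters as two terms: each swallow's deviation from that participant's own mean pressure, and the participant mean. State that the model has a participant random intercept, and that the adjusted stimulus effect is read from this model. The two pressure slopes then show directly whether they differ.

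Fit this model on participants with concurrent palate pressure and report how many that is. State that those on the IOPI fallback have no swallow-level value and so do not contribute to Question 3.

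Cost: one derived variable, one extra model term, and one person-level degree of freedom out of 10-12 participants. No new data are needed, and if the slopes agree the answer is essentially unchanged.

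### Aim 3 asks whether starch versus gum changes the Aim 1 and 2 results, but its analysis describes only adherence and acceptance: the contrast is not isolated for timing and residue and not stated for aspiration

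*Combined protocol and SAP*

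**What the plan says.** Section 2 (Purpose and Specific Aims) words Aim 3 as: "To determine whether the use of starch vs. gum thickeners impact the results of aims 1 and 2". It adds that salivary flow is collected "to control for possible interactions between thickener type and oral dryness on the results".

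Section 3, Data Analysis, treats the outcomes as follows.

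- **Aim 1, palatability.** Hedonic ratings are compared across stimuli by ANOVA, with a stated expectation that gum will be preferred to starch.
- **Aim 2, aspiration.** A chi-square analysis sets thin liquids against thickened liquids. Starch and gum are not mentioned separately.
- **Aim 2, timing and residue.** Linear mixed models are fitted with stimulus as the one named factor. The Saxon saliva result is a covariate in all analyses, with its place in the model referred to a figure that is missing from the available text.
- **Aim 3.** "For Aim 3, we will use qualitative methods to describe participant reports of adherence to the prescribed thickener". A second sentence uses the Session 1 quality-of-life and performance scales to understand acceptance.

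The adherence reports come from calls that not everyone makes: "For those willing to participate, this optional experiment will involve two follow-up telephone calls". The videofluoroscopy schedule is "3 boluses each of 5 stimuli, for a total of 15 boluses". Saliva is taken once at the start of each session: "Prior to data collection, saliva flow will be collected using the Saxon Test".

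**The concern.** The paragraph labelled Aim 3 does not answer the Aim 3 question. It describes how participants who take the calls report using the product they were given. It does not compare what happened on starch with what happened on gum. If the team follows the plan literally, three things are left open.

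- **Timing and residue.** A test of the stimulus factor shows that some stimuli differ. It does not show whether thickener type is the reason.
- **Aspiration.** Pooling the thickened liquids gives no starch result and no gum result. Yet section 4 (Benefits) hands out cans of the particular thickener type that helped a participant.
- **Saliva.** The interaction given as the reason for measuring saliva has no model term in the readable text.

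**Working it through.** **1. Stimulus structure.** The plan's own count reproduces: 5 stimuli × 3 boluses = 15. The five stimuli are not listed. Two thickeners at two consistencies plus thin gives 2 × 2 + 1 = 5, so I infer that layout. A five-level factor has 4 degrees of freedom: thin versus thickened, consistency, thickener, and consistency × thickener. Starch versus gum is one of the four.

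**2. What the overall stimulus test loses.** Suppose only thickener matters. Assume two-sided 0.05, sphericity, and an effect of 0.75 residual SD of a stimulus mean.

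| n | Power, 1-df thickener contrast | Power, 4-df stimulus test |
|---|---|---|
| 10 | 0.64 | 0.39 |
| 12 | 0.72 | 0.48 |

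**3. Precision of gum-minus-starch with complete data.** Units are the SD of the within-participant difference. Assume two-sided 0.05 and 80% power; the plan states neither. The 95% half-width is t(0.975, n−1)/√n. The detectable difference d solves P(T > t) = 0.80, where T is noncentral t with n−1 df and noncentrality d√n.

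- n = 10: half-width 2.262/3.162 = 0.72; d = 1.00.
- n = 12: half-width 2.201/3.464 = 0.64; d = 0.89.

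**4. Saliva as an additive covariate.** Write S for a participant's Saxon value in a session. An additive model adds βS to every stimulus in that session, so in gum-minus-starch it cancels: βS − βS = 0. An interaction makes the difference δ + γS, and only a thickener × Saxon term estimates γ. In complete, balanced data this is algebra and needs no simulation. Detecting the interaction with 80% power would need a correlation of about 0.76 (n = 10) or 0.71 (n = 12) between saliva and the paired difference.

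**5. How many participants receive both thickeners.** This depends on whether testing stops at aspiration, and the protocol points two ways. Section 4, Risks (e), ends the session when aspiration is seen. Section 4, Benefits, describes participants who aspirate and also show safer swallows on thickened stimuli. I therefore ran each reading: five blocks of three boluses in random order, equal starch and gum risk, and between-participant log-odds SD 1.0. All risks are assumed per-bolus values for a median participant.

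| Thin / thickened risk | Any aspiration ends testing | Only thickened aspiration ends it | None ends it |
|---|---|---|---|
| 0.05 / 0.025 | 80% | 87% | 100% |
| 0.10 / 0.05 | 67% | 77% | 100% |
| 0.20 / 0.10 | 51% | 62% | 100% |
| 0.30 / 0.15 | 40% | 52% | 100% |

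Reading the risks as population averages instead raises the first results column to 86%, 75%, 58% and 46%. The table leaves out two further losses: the two-minute exposure bell in Risks (d), and the rule that participants with safe thin swallows "will be withdrawn from the study".

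**6. Aspiration by thickener, one illustration.** Take n = 10, risks 0.20/0.10, and stopping at any aspiration. About 70% are exposed to each thickener, or 7 people, with 0.27 × 10 = 2.7 expected events on each. For 3 of 7 the exact (Clopper-Pearson) 95% interval is 10% to 82%.

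**The case against.** The best defence is that this is a 10-12 person feasibility study and that most of Aim 3 can be recovered from the plan. Much of that stands, and it rules out several stronger readings a reader might infer.

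- **That the plan contains no thickener comparison.** It does: palatability has a directional gum-versus-starch hypothesis.
- **That the contrast cannot be estimated, or could be freely invented afterwards, for timing and residue.** Both thickeners are used, stimulus is a factor, and Aim 3 itself names starch versus gum. What is open is the form of the contrast, such as pooled or by consistency.
- **That adherence is irrelevant to Aim 3.** The aim's significance statement mentions compliance, and acceptance is part of Aim 1. The adherence description belongs, but it is not enough.
- **That the saliva analysis is shown to be wrong.** The covariate structure is referred to a figure that is not available. An interaction path there cannot be excluded, and the word covariate does not by itself mean additive.
- **That only about half the participants will have both thickeners.** That follows from one reading of the stopping text and one set of assumed risks. Nor would a paired calculation on those few people describe a mixed model, which also uses incomplete sessions.

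The defence does not reach aspiration. No reading of the available text gives a starch-versus-gum aspiration result. Small numbers are a reason to report estimates with intervals; they do not justify leaving part of a stated aim without an estimate.

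**Conclusion.** The point holds on the text. The analysis labelled Aim 3 does not address the Aim 3 question, the aspiration comparison by thickener is missing, and the timing and residue contrast is available but not isolated. The saliva part is conditional on the missing figure: if the covariate is additive, a once-per-session value cannot model the interaction.

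Severity is minor to moderate for a feasibility pilot. The degrees-of-freedom argument rests on the inferred thin-plus-2×2 layout. The precision figures rest on complete data and on assumed alpha and power. The share of participants with both thickeners runs from about 40% to 100%, and the reading of the stopping text moves it at least as much as some of the assumed risks do.

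**What to change.** 1. **Timing and residue.** In the mixed models, code the thickened stimuli as thickener (starch, gum) by consistency (slightly, mildly thick), with thin as reference. Name gum-minus-starch as the Aim 3 estimate, with a confidence interval.
2. **Aspiration.** Report starch and gum separately, as events over boluses given and over participants exposed. Give exact intervals for the participant proportions, and state how many received both thickeners. The denominators can be counted, because "the videofluoroscopy recordings will be spliced into single bolus clips".
3. **Saliva.** Unless the figure already shows it, add an exploratory Saxon-by-thickener term to the timing, residue and palatability models, using the same session's Saxon value and reported with an interval. None is suggested for aspiration, where events would be too few.
4. **Adherence.** Keep the description, split by thickener type, as a supplement.
5. **Stopping text.** Reconcile Risks (e) with Benefits in section 4, since the two imply different numbers of participants with data on both thickeners.

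Alternatively, narrow Aim 3 to what is analysed.

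Items 1 to 4 change analysis wording only and need no new data. The price is that the estimates will be imprecise, the interaction most of all, so they should be presented as estimates with intervals and not as tests of efficacy.
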